# For time to event endpoints:

Kaplan-Meier estimates will be provided including at least median survival and its 95% CI on the combined EDP-938 and placebo for Parts 1 and 2. Kaplan-Meier plots will also be provided. Generalized Wilcoxon test will be performed to compare the EDP-938 vs Placebo. If appropriate, log-rank test will be performed as well. If required, a Cox proportional hazards model, adjusting for associated baseline assessment (if appropriate), would be considered. Subjects who did not achieve the specified event will be censored as follows:

RSV RNA viral load:

• Subjects who have not been followed through the Day 14 visit (discontinued from the study or incomplete follow-up) or completed Day 14 visit will be censored at Day 14 visit date.

Parent/Guardian ReSVinet, Professional ReSVinet, Parent/Guardian RESOLVE-P, Caregiver Global Impression of Severity (CaGI-S), Caregiver Global Impression of Change (CaGI-C):

• Subjects who have not been followed through the Day 14 visit (discontinued from the study or incomplete follow-up) or completed Day 14 questionnaire will be censored at Day 14.

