# Secondary Endpoints

• Safety and tolerability of EDP-938 compared to placebo as assessed by, but not limited to, AEs, vital signs, and clinical laboratory results;

- AUC for RSV RNA viral load measured in nasal swab samples by RT-qPCR;
- Proportion of subjects with RSV RNA viral load below the LOD in subjects receiving EDP-938 compared to placebo;
- Time to RSV RNA viral load being undetectable;
- PK parameters of EDP-938 including AUC and predose concentrations;
- Time to discharge for hospitalized subjects;
- Time to use of oxygen for hospitalized subjects who are not receiving oxygen at the time they receive the first dose of study drug;
- Proportion of hospitalized subjects requiring oxygen supplementation or have an increased oxygen requirement;
- Time to mechanical ventilation for hospitalized subjects;
- Proportion of hospitalized subjects requiring mechanical ventilation;
- Deaths among hospitalized subjects;
- Time to hospitalization for initial outpatients who are subsequently hospitalized;
- Proportion of outpatients who are subsequently hospitalized or died;
- Time to resolution of symptoms for outpatients who are not hospitalized.

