# 4.2 Sample Size Considerations

No formal hypothesis testing is planned for Parts 1 or 2 of this study. Therefore, no formal sample size justification is provided. Approximately 90 subjects will participate in this study: 12 subjects are planned in each cohort of the age groups in Part 1 (24 subjects in each age group). In Part 2, 20 subjects are planned in each of the age groups. Additional subjects may be added based on SSC recommendations.

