# 4.8 Demographic and Baseline Characteristics

No statistical testing will be performed for the comparison between treatment groups on demographics and baseline characteristics. Subject demographics and baseline characteristics will be summarized descriptively using the Safety Population.

Age, Gestational Age, Body Length, Head Circumference, and Weight, RSV viral load measured by RT-qPCR (log10 copies/mL), professional and parent/guardian ReSVinet total scores, RESOLVE-P domain and composite scores, CaGI-S total score collected at baseline, and duration of RSV symptom onset (from the first sign of respiratory infection to randomization) will be summarized.

Qualitative variables such as sex, ethnicity, race, RSV type (RSV-A, RSV-B), and pathogen will be summarized using descriptive statistics. A by-subject listing will be provided.

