# 4.13.5 Efficacy Analysis for Pooled Population

The primary endpoint is the daily change in RSV shedding in nasal swab samples determined using RTqPCR from baseline through the treatment phase in the pooled population (subjects from Parts 1 and 2 together).

All secondary efficacy endpoints described in *Section 4.13.4*, as well as all exploratory endpoints described in Section 4.13.7 are also the secondary and exploratory endpoints for the pooled population and will be analyzed with the pooled data from both Parts 1 and 2.

All pooled efficacy data will be summarized descriptively by EDP 938 and Placebo for each age group and combined EDP 938 and Placebo, as described in *Section 4.13.4* and *Section 4.13.7*.

Inferential statistics analysis will be performed to detect treatment effects of EDP 938 and Placebo using the Efficacy Population, mITT-3 and mITT-5 for the following RSV RNA viral endpoints as well as RSV symptom related endpoints described in *Section 4.13.7* (except for RESOLVE-P where Efficacy Population is used)

- Daily change in RSV shedding in nasal swab samples determined using RT-qPCR from baseline through treatment phase
  - Absolute change from baseline in RSV RNA viral load (outcome variable) will also be analyzed using MMRM as described below.
  - AUC for RSV RNA viral load measured in nasal swab samples by quantitative reverse transcription polymerase chain reaction (RT-qPCR) will be estimated via MMRM.
- Time to RSV RNA viral load being undetectable

Time to RSV RNA viral load being undetectable (TND) will be analyzed using two approaches as defined below:

- Time to RSV RNA viral load being undetectable (days) is defined as the time between the date of first dose to the first date during post-dose period of achieving RSV RNA viral load TND after which no further samples have detectable RSV RNA viral load. Subjects with baseline RSV viral load TND will be excluded from the analysis.
- Time to confirmed undetectable RSV RNA viral load (days) is defined as the time between the date of first dose to the first of 2 consecutive post-baseline time points of achieving RSV RNA viral load TND. Subjects with baseline RSV viral load TND will be excluded from the analysis.

Inferential statistics analysis approaches are as follows:

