# For continuous endpoints with multiple timepoints:

Absolute change from baseline in the outcome of interest (outcome variable) will be analyzed using a mixed-effect model for repeated measures (MMRM) to compare EDP-938 and Placebo.

The model includes treatment group (EDP-938, placebo) and Day (all scheduled post-baseline timepoints available) as fixed effect, associated baseline (as appropriate), and treatment group-by-Day interaction term as factors. Treatment groups will be compared at scheduled post-baseline timepoints of interest. An unstructured covariance matrix will be imposed. If the unstructured covariance matrix fails to converge, then the following covariance structure will be assessed in this order: autoregressive, compound symmetry, Toeplitz. The Satterthwaite approximation will be used to estimate the denominator degrees of freedom. The least-squares means and two-sided 95% CIs of absolute change from baseline at each post-baseline timepoint will be derived via this model. The least-squares means and two-sided 95% CIs of AUC through Days 3, 5, 9 and 14 will be presented for individual groups and the difference between groups. The p-value will be presented for the difference between treatment groups at each post-baseline timepoint.

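### The only committed test of time to undetectable RSV RNA ignores baseline viral load; one baseline-adjusted comparison should be fixed before unblinding

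*SAP*

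**What the plan says.** "Time to RSV RNA viral load being undetectable" is a secondary endpoint for Part 2 and the pooled population (SAP 3.2.2). SAP 4.13.5 gives it two definitions, sustained and confirmed, and plans inferential comparison in the Efficacy, mITT-3 and mITT-5 populations. SAP 4.13.6 repeats the analysis in children who received the final selected doses.

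The time-to-event paragraph of SAP 4.13.5 provides, in order:

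- Kaplan-Meier estimates, followed by the one firm commitment to a test: "Generalized Wilcoxon test will be performed to compare the EDP-938 vs Placebo".
- A second test, conditional and again with no covariate named: "If appropriate, log-rank test will be performed as well".
- Baseline adjustment, offered only as a possibility: "If required, a Cox proportional hazards model, adjusting for associated baseline assessment (if appropriate), would be considered".

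Only the first test is unconditional. The Cox sentence does not say when the model is required or who decides.

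Elsewhere, baseline viral load is used as follows:

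- In the endpoint definition it acts only as an exclusion: "Subjects with baseline RSV viral load TND will be excluded from the analysis".
- It is summarized as a baseline characteristic (SAP 4.8).
- The mixed model for change from baseline, in the same section, lists "associated baseline (as appropriate), and treatment group-by-Day interaction term as factors".

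Randomization is described by part, cohort and age group (SAP 2.2, protocol 5.6). No stratification by viral load is described.

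**The concern.** Time to undetectable is the time a child takes to fall from a personal starting level to a fixed limit. A child who starts higher has further to fall. The plan collects that starting level and allows for it in the mixed model for the same assay, but leaves it out of the one clearance test it commits to.

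Two things are at stake. First, if baseline predicts clearance, the unadjusted test carries variation that an adjusted test would remove. Second, with a placebo arm of about 24, the arms can easily differ at baseline by chance, and the unadjusted result moves with that difference. Because the adjusted model is optional and has no trigger, the choice to run it could be made after the imbalance and the unadjusted result are known.

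**Working it through.** **Planned numbers.** Part 1: 2 age groups × 2 cohorts × 12 = 48, at 2:1, so 32 EDP-938 and 16 placebo. Part 2: 2 × 20 = 40, at 4:1, so 32 and 8. Pooled: 88 children, 64 versus 24, which agrees with the approximately 90 in SAP 4.2. The SAP gives no power, effect size, event count or alpha for this endpoint, so there is no stated figure to reproduce. A two-sided 5% level is assumed.

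**Why baseline should matter.** The limits in SAP 4.13.2 are log10(620) = 2.79 for RSV A and log10(80) = 1.90 for RSV B. For RSV A, a child starting at 8 log10 must fall 8 − 2.79 = 5.21; a child starting at 4 must fall 4 − 2.79 = 1.21. At an assumed 0.45 log10/day that is 5.21/0.45 = 11.6 days against 1.21/0.45 = 2.7 days. Differences in decline rate between children and assay noise both weaken this link.

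**Chance imbalance.** The SE of the difference in baseline means is √(1/64 + 1/24) = 0.239 SD. The probability of a difference above 0.25 SD in either direction is 2 × [1 − Φ(0.25/0.239)] = 30%; above 0.5 SD it is 3.7%. At an assumed baseline SD of 1.5 log10, one SE is 0.36 log10, worth 0.36/0.45 = 0.8 day of clearance.

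**Simulation by strength of prognosis.** Assumed: 64 v 24, log-normal clearance time with control median 9 days and SD 0.6 on the log scale, clearance 30% faster on drug, events seen only at the nominal Day 3, 5, 9 and 14 swabs, 1000 trials per setting (Monte Carlo SE about 1.5 points). R² is the share of variance in log clearance time explained by baseline. Cox models use Efron ties.

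| R² | Wilcoxon, unadjusted | Cox, unadjusted | Cox, baseline-adjusted |
|---|---|---|---|
| 0 | 60% | 52% | 52% |
| 0.10 | 62% | 54% | 58% |
| 0.25 | 62% | 55% | 67% |
| 0.50 | 60% | 53% | 77% |
| 0.70 | 55% | 47% | 89% |

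Like for like (Cox with and without baseline), adjustment gains 0 to 4 points at R² of 0.10 or less, about 12 at 0.25, 25 at 0.50 and 42 at 0.70. Overall type I error was 3.4% to 6.1% across all tests.

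The unadjusted Wilcoxon result depends on which arm starts higher. At R² = 0.50 its power is about 14% if the EDP-938 arm starts more than 0.25 SD higher and 98% if it starts more than 0.25 SD lower. At R² = 0.25 these are 35% and 85%. At R² = 0 they are 65% and 63%, so there is no such dependence.

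**Simulation of viral decline, with the same Wilcoxon test stratified by baseline tertile.** Swabs at 2, 4, 8 and 13 days after first dose. The gain from stratifying ran from about 1 to 5 points when decline rates varied widely between children to 20 to 35 points when they varied little. A further grid (baseline mean 6 log10, SD 1.2 to 1.5, decline 0.40 log10/day, drug adding 0.12, between-child slope SD 0.05 to 0.30, assay noise 0.3 to 0.8) gave 3 to 41 points: 6 to 13 at slope SD 0.20 and 3 to 5 at 0.30. Overall size stayed near 5% for both tests. When the arms differed by more than 0.25 SD at baseline, the unstratified test rejected a true null about 7% to 15% of the time.

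**The case against.** The strongest reply has four parts.

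- **The plan already names a baseline-adjusted model.** True, and a reader who inferred that adjustment is absent would be wrong. What is missing is commitment: there is no trigger, and the covariate is described only generically.
- **The endpoint is one of many secondary endpoints, and nothing was powered.** This stands. SAP 4.2 says "No formal hypothesis testing is planned for Parts 1 or 2 of this study", and protocol 11.2 calls the methods primarily descriptive. The documents do not call this a key endpoint, and no claimed power is being lost. But SAP 4.13.5 does plan between-arm tests on pooled data, and a planned test should be a well-chosen one.
- **The documents do not show that baseline governs clearance.** Also right. A reader might infer that baseline viral load largely determines clearance time, so that the test must lose much of its power. No section gives the strength of the relation, and the gain is small if decline rates differ greatly between children.
- **Events on four visit days might seem to rule out a Cox model because of ties.** The documents do not support that. Visits have windows and times run to actual dates, so ties are fewer than four fixed days would imply, and the Efron-tied Cox model kept its size in the check above.

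One practical objection also stands. The time-to-undetectable rule excludes children undetectable at baseline but is silent on a missing baseline, whereas the AUC rule in SAP 4.13.2 excludes both. An adjusted analysis needs a rule for missing values.

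**Conclusion.** The concern holds in a limited form. The only committed test for this secondary endpoint is unadjusted, and the adjusted alternative is left open. The size depends on an assumption that the documents do not settle: how strongly baseline viral load predicts clearance. Under the assumed inputs, the power forgone ranges from about 1 to 5 points to 20 to 35 points.

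A reader might infer that omitting baseline inflates the false-positive rate. Overall it does not. The effect is conditional: about 7% to 15% when the arms differ by more than 0.25 SD, an imbalance that has a 30% chance of occurring at 64 versus 24.

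Stratifying the planned test did not lose power in the settings examined. Replacing it with Cox could cost some if baseline turned out not to be prognostic (52% against 60% at R² = 0 in the table). The case for the change is that it is nearly free and removes a post hoc choice; no stated figure in the plan is wrong.

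**What to change.** In SAP 4.13.5, before unblinding, commit to one baseline-adjusted comparison for both time-to-undetectable definitions:

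- **Either** stratify the generalized Wilcoxon test by tertile of baseline log10 viral load, with cut points set on blinded pooled data; this keeps the sponsor's chosen test. **Or** use a Cox model with baseline log10 viral load as covariate and a stated method for ties.
- Delete the conditional wording on the Cox model and report the baseline-adjusted hazard ratio routinely as the effect size.
- Exclude children with a missing baseline viral load, as the AUC rule in SAP 4.13.2 already does.
- Keep the unstratified generalized Wilcoxon test as supportive.

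The cost is SAP wording and minor programming, with no change to protocol procedures or data collection. The downside is sparse strata: tertiles leave about 24/3 = 8 placebo children each in the full set, and fewer in mITT-3 and the final-dose analysis, where some strata may contribute little.

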The RSV RNA viral load AUC will be calculated using the trapezoid rule [2]. The AUC will require at least 2 non-missing data points. Subjects with missing or undetectable RSV RNA viral load at baseline will be excluded from the analysis. The AUC will be calculated based on all available assessments collected on Days 1/Baseline, 3, 5, 9, and 14 and the actual date/time of each assessment will be used for the calculation. For the baseline viral load (Day 1), time is set as 0. For each assessment post first dose, the actual time in days is computed as difference between the date/time of the assessment and the date/time of the first dose. The AUC is also standardized for 14 days by multiplying 14/tlast where tlast is the actual time in days of the last available assessment. Additionally, the AUC from Day 1 through Day 3, the AUC from Day 1 through Day 5, and the AUC from Day 1 through Day 9 will be also derived and standardized similarly as for AUC from Day 1 though Day 14.

Descriptive statistics for RSV RNA viral load AUC will include, at a minimum, the number of non-missing measurements, mean, standard deviation, median, minimum, 25th percentile, 75th percentile, maximum, and 95% CI for the mean.

- Daily change in RSV shedding in nasal swab samples determined using RT-qPCR from baseline through the treatment phase
  - RSV RNA viral load observed and change from baseline will be summarized by visit (Baseline, Days 3, 5, 9 and 14). The summary statistics will include, at a minimum, the number of non-missing measurements, mean, standard deviation, median, minimum, 25th percentile, 75th percentile, maximum, and 95% CI for the mean.

Line graph of RSV RNA viral load will be produced:

- (1) Observed mean viral load  $\pm$  95% confidence interval by days (1, 3, 5, 9 and 14) for each treatment group and age group.
- Time to RSV RNA viral load being undetectable

Time to RSV RNA viral load being undetectable (TND) will be analyzed using two approaches as defined below:

- Time to RSV RNA viral load being undetectable (days) is defined as the time between the date of first dose to the first date during post-dose period of achieving RSV RNA viral load TND after which no further samples have detectable RSV RNA viral load. Subjects with baseline RSV viral load TND will be excluded from the analysis.

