# Final dosing regimen:

Subjects who received the final selected doses (7.5 mg/kg in subjects in 12 to  $\leq$ 36 months and 5 mg/kg in subjects <12 months) will be included in the following analyses.

- Daily change in RSV shedding in nasal swab samples determined using RT-qPCR from baseline through the treatment phase
  - Absolute change from baseline in RSV RNA viral load (outcome variable) will also be analyzed using MMRM as described in *Section 4.13.5*.
  - AUC for RSV RNA viral load measured in nasal swab samples by quantitative reverse transcription polymerase chain reaction (RT-qPCR) will be estimated via MMRM.
- Time to RSV RNA viral load being undetectable
  - The analyses are outlined in the time to event analyses as described in *Section 4.13.5*.

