 Subjects who discontinue treatment early (before completing 5 days of dosing) should return to the study site within 24 hours following the last dose of study drug for an EOT visit. Follow-up visits will be scheduled 4 days (PT1, Day 9), 9 days (PT2, Day 14), and 23 days (PT3), Day 28 [EOS]) after the last dose of study drug was administered. Assessments should be performed as indicated, respectively for the Day 9 (PT1), Day 14 (PT2), and Day 28 (EOS/PT3) visit. Subjects who discontinue the study early (before Day 28) should return to the study site within 24 hours and no more than 48 hours later to complete the EOS procedures.

 If multiple assessments are scheduled for the same timepoint, it is recommended that noninvasive procedures being done before more invasive procedures, e.g., first complete eCOA (parent/guardian and clinician eCOAs could be concurrent), then ECG, then vital signs/SpO2, then nasal swab and finally blood draw.

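### SAP 4.13.5 censors event-free children who leave before Day 14 at a Day 14 visit date they do not have (viral load) or at a fixed Day 14 (scores), an unlabelled assumption that leavers did not clear

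*SAP*

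**What the plan says.** The censoring rule in SAP 4.13.5 (time-to-event endpoints) begins "Subjects who did not achieve the specified event will be censored as follows". For viral load it names "Subjects who have not been followed through the Day 14 visit" and goes on: "discontinued from the study or incomplete follow-up) or completed Day 14 visit will be censored at Day 14 visit date". Early leavers and completers therefore share one censoring time. The parallel sentence for the ReSVinet, RESOLVE-P and CaGI endpoints ends "or completed Day 14 questionnaire will be censored at Day 14".

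The rule feeds the Kaplan-Meier medians and plots, the generalised Wilcoxon test, and the optional log-rank test and Cox model. For time to undetectable RNA these are run in the Efficacy, mITT-3 and mITT-5 populations. That endpoint has two definitions: undetectable with no later detectable sample, and a confirmed version dated at "the first of 2 consecutive post-baseline time points of achieving RSV RNA viral load TND".

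Four other places bear on the point:

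- **SAP 7.1, footnote 5.** A child who leaves the study before Day 28 "should return to the study site within 24 hours and no more than 48 hours later to complete the EOS procedures". The schedule shows nasal swabs at V1, V3, V5, PT1 and PT2, and none at PT3/EOS.
- **SAP 4.13.6, final dosing regimen.** "The analyses are outlined in the time to event analyses as described in" Section 4.13.5, so the rule carries over.
- **SAP 4.3.** In general, missing data are not imputed and summaries use observed data.
- **SAP 4.13.2, viral load AUC.** A last time point is already derived, which "is the actual time in days of the last available assessment".

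**The concern.** For viral load the rule cannot be computed as written for a child without a Day 14 visit. The programmer must either leave the time missing and lose the child, or put in a nominal Day 14. For the scores, Day 14 is given outright.

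With a nominal Day 14, a child last swabbed on Day 5 and still detectable stays in the risk set on Days 9 and 14 as if seen and found not cleared. Compared with censoring at the last assessment, the estimated event probability can then only be equal or lower. It is too low if leavers would have cleared like those who stayed. Medians can shift or become not reached, and if early dropout differs clearly between arms the comparison is distorted. The analyses in SAP 4.13.6 vary dose, steroid use and coinfection, but never the censoring.

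**Working it through.** **Plan's own figures.** Headcount: 4 × 12 + 2 × 20 = 88, which agrees with approximately 90 (SAP 4.2). Taking Cohort 2 as 2:1, like the rest of Part 1, EDP-938 has 4 × 8 + 2 × 16 = 64 and placebo 4 × 4 + 2 × 4 = 24. The documents give no dropout rate, clearance rate, power or alpha for these endpoints.

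**Assumed inputs.** Cumulative clearance F = 8, 22, 45 and 70% by the swabs on Days 3, 5, 9 and 14. A fraction d leaves at random after a given swab. Leavers would clear like stayers. All PT2 swabs fall on Day 14.

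**First definition, leavers censored at nominal Day 14.** Nobody is censored before Day 14, so the estimate is F(k) + (1 − d)(0.70 − F(k)), where k is the last swab before leaving.

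| d | Leave after Day 5: 0.22 + (1 − d)(0.48) | Leave after Day 9: 0.45 + (1 − d)(0.25) |
|---|---|---|
| 5% | 67.6% | 68.75% |
| 10% | 65.2% | 67.5% |
| 20% | 60.4% | 65.0% |

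Censoring at the last swab returns 70% in every row. Other assumed clearance curves, with children leaving after Day 3, 5 or 9, gave an understatement of 1.0 to 15.3 percentage points.

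**Median.** It becomes not reached when d > (F14 − 0.5)/(F14 − F5). For the inputs above this is 0.20/0.48 = 42%. With 15% cleared by Day 5 and 55% by Day 14 it is 0.05/0.40 = 12.5%.

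**Confirmed definition.** A Day 14 swab cannot be the first of two, so the target is 45%. With 20% leaving after Day 5:

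- nominal Day 14: 0.08 + 0.8 × 0.37 = 37.6%;
- last swab: 1 − (0.92 − 0.14 × 0.8)(0.55/0.78) = 43.0%;
- last swab that has a later swab: 45%.

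With 20% leaving after Day 9, both of the first two rules give 0.22 + 0.8 × 0.23 = 40.4%, and the third again gives 45%. For this definition, censoring at the last swab is not enough.

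**Test size.** Simulated for the first definition with 64 versus 24 children, no effect, and two-sided 0.05 (assumed), with unequal dropout run in both directions.

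| Dropout | Nominal Day 14 | Last swab |
|---|---|---|
| Equal 10% or 20% | 0.048–0.054 | 0.047–0.054 |
| 5% v 10%, after Day 5 | 0.053–0.054 | 0.051–0.052 |
| 5% v 20%, after Day 9 | 0.053–0.060 | 0.051–0.053 |
| 5% v 20%, after Day 5 | Wilcoxon 0.073–0.076, log-rank 0.082–0.089 | 0.052–0.054 |

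Repeat runs of the last row, some with other clearance curves, gave about 0.06 to 0.09 under nominal Day 14 and 0.045 to 0.056 under last-swab censoring. At 20% in placebo and 5% in EDP-938, the last row means about 5 of 24 and 3 of 64 children lost.

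**Should the new censoring date be capped at Day 14?** PT2 may fall on Days 12 to 16 (SAP 4.5 and 7.1). Spread it evenly, with no dropout, 45% cleared by Day 9 and 70% by PT2. On each of the five days 5% of children have the event and 6% attend without it.

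- Actual dates: survival is 0.55 × (0.50/0.55) × (0.39/0.44) × (0.28/0.33) × (0.17/0.22) × (0.06/0.11) = 0.16, so 84% by Day 16.
- Event-free children capped at Day 14: only children with events remain at risk after Day 14, so the curve reaches 100%.

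Capping is therefore harmful.

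**The case against.** **The group may be small.** Protocol 7.3 has the investigator ask children withdrawn by their caregiver to return for EOT, PT1 and PT2, and PT1 and PT2 include swabs. Home visits are allowed (Protocol 7.1), and contact attempts follow a missed EOT or EOS visit (Protocol 7.3.2). This stands. It limits the number but does not remove the problem: a return visit is only requested, and children lost to follow-up or with consent withdrawn give no later data.

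**Last-assessment censoring is also an assumption.** It takes leaving to be unrelated to clearance, yet Protocol 7.3.1 lists adverse events and lack of efficacy among the reasons for discontinuation. If leavers would not have cleared, the Day 14 rule gives the right answer. This stands, and is why that rule should be kept as a labelled sensitivity analysis.

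**The percentages are idealised.** A reader might infer that under the present rule the Kaplan-Meier value at Day 14 is always events divided by N. That holds only if every PT2 swab falls on one day, because completers are censored at their actual date. In the even-spread example above, with no dropout at all, the Day 14 value is 62%, not 70%. This stands as a limit on the figures.

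**SAP 4.3 might be read as covering the gap,** since it completes partial dates conservatively for time calculations. A visit that never took place has no partial date, and for the scores the rule is explicit. This does not stand.

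**No decision depends on it.** SAP 4.2 plans no formal hypothesis testing for Parts 1 or 2. SAP 4.13.5 does plan inferential tests on the pooled data, so the results will be read, but the point remains one about secondary and exploratory endpoints.

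**Conclusion.** The point holds in limited form. The rule is undefined for viral load, and for the scores it counts unobserved days as event-free. Neither document calls this a worst-case strategy. The children affected are those without a PT2 assessment, an unknown and perhaps small number.

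Under the assumed inputs, clearance is understated by about 2, 5 or 10 points with 5, 10 or 20% leaving after Day 5, and by less if they leave after Day 9. The test is distorted materially only when early dropout differs clearly between arms. The calculations concern viral load. The size for the score endpoints was not worked out, because their definitions in SAP 4.13.7 are not in the public text.

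A reader might infer that the primary result is at risk, or that the arm comparison is biased in general. The documents support neither. The primary endpoint is change in viral load analysed by MMRM, which does not use this rule, and with equal dropout test size is kept. Nor do the documents show that a nominal Day 14 will be used for viral load; it is one of two ways to fill the gap.

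**What to change.** In SAP 4.13.5, before unblinding:

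1. Censor event-free children at the actual date of their last evaluable swab (viral load) or last completed diary or score (symptoms), up to and including the PT2/Day 14 assessment. For children who attended PT2, use the actual PT2 date.
2. Do not truncate at Day 14. Capping only event-free children, while events on Days 15 and 16 keep their dates, biases the curve upwards.
3. For events defined as the first of 2 consecutive time points, censor at the last assessment that is followed by another one.
4. Keep the present approach as a sensitivity analysis labelled 'leavers counted as not cleared'. There, give leavers a defined end-of-follow-up date no earlier than the last event time.

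The first item also covers a child who stops drug on Day 1 or 2. PT2, 9 days after the last dose, then falls on Day 10 or 11, inside the Day 9 analysis window (Days 8 to 11, SAP 4.5).

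The cost is a few lines of SAP text and standard programming. No new data are needed, since the last viral load time is already derived for the AUC. The downside is slightly fewer children at risk near Day 14.
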